### **D3.7. Data Management and Analysis**

**D3.7.1. Data Management.** Participant recruitment and contact information will be input through screens created by the Data Systems Team within Moffitt's Research Computing Support Group (Research IT) and will be subject to computerized range and consistency checks. The data will then populate an Access database, which will also be created and maintained by Research IT. This process will be supervised jointly by the PI and Study Data Manager/Biostatistician. Paper-and-pencils surveys will be entered into database files with computerized range and consistency checks. Online surveys will have range checks built into the survey items, as appropriate. The survey databases will be converted on a monthly basis to an analysis database. This analysis database and SAS version 9.4 (SAS Institute, Cary, NC) will be used by the statistician who will provide the PIs with reports and summaries on a regular basis and perform the final analyses.

**D3.7.2. Sample Size and Study Power Analysis.** The primary statistical analyses will assess the efficacy of the full intervention (SS-SP) in producing smoking cessation compared to Usual Care (UC) in two ways: (1) across all 4 follow-ups using generalized estimating equations (GEE), and (2) at the 24-month follow-up using logistic regression. The estimated 7-day point prevalence abstinence rates for this study were based on the cessation study (C1.2.3, Table 1) with an adjustment of 0.625 standard error units to decrease group differences. For the four follow-ups, the estimated abstinent rates are 12.3%, 15.2%, 19.1%, & 19.8% in the UC condition and 15.2%, 23.0%, 26.9%, & 28.8% in the SS-SP condition. Power was targeted to be  $> .80$  with alpha=.05 and a 2-sided test. Using GEESIZE version 3.1 (Rochon, 1998; Dahmen 2004) with an AR(1) working correlation structure and coefficient of 0.7, sample size was estimated at 322/group for the GEE analyses. For the logistic regression at 24 months, sample size was estimated at 365/group. All analyses will be completed following multiple imputation to manage missing data (below). Therefore, no adjustments of

enrollment size will be needed to account for attrition. The final sample size for analyses was rounded up to 370 per group. An additional 500 participants will be recruited from the state of Florida.

We initially planned to enroll 1240 individuals, 740 nationally and 500 in Florida. However, due to higher-than-expected attrition, we are increasing our overall sample size to 1400 individuals, 850 nationally and 550 in Florida.

**D3.7.3. Data Analysis Overview.** Analyses will be conducted with SAS version 9.4 and Mplus Version 7 (Muthén & Muthén, 2008). Frequency distributions and contingency table analyses will be used as a point of departure for more advanced analyses. Group differences in baseline measures will be assessed and any variable that exhibits a significant group difference will be incorporated into the primary analyses.

To manage missing data, multiple imputation under the Missing at Random assumption will be applied using a Markov Chain Monte Carlo method (Schafer, 1997) via PROC MI in SAS, given the expected large number of non-monotonic missing data patterns and the expected large number of auxiliary variables (e.g., baseline measures that predict smoking status at follow-up) to be determined by preliminary analyses. A post hoc approach (Rubin, 1987) will address the influence of Missing Not at Random (MNAR) on smoking status (i.e., missing is due to smoking). Sensitivity analyses will be performed by comparing results from different multiple imputation data sets that were generated using different levels of MNAR influence.

**D3.7.4. Analytic Plan for Addressing Specific Aims.** All analyses will be performed on complete data sets following multiple imputation using all 1400 participants.

**Specific Aims 1.** All analyses will be performed on complete data sets following multiple imputation. Generalized estimating equations (GEE) will be used to fit population-averaged models of the longitudinally measured 7-day point prevalence, with the main covariates of intervention condition (UC vs. SS-SP), time (months from baseline), and the interaction of condition and time. The GEE analysis will allow for assessment of changes in abstinent rates over time and group differences in changes. Logistic regression will be used to assess condition differences at the 24-month (final) follow-up, which is 6 months after the SS-SP intervention. In both the GEE models and logistic regression, potential confounding variables (e.g., group differences on demographic variable) that appear despite randomization will be included.

**Secondary Aim.** The secondary aim is to assess prospective moderators of the expected intervention effect (e.g., gender, SES, quitting motivation, nicotine dependence, *country of origin*, acculturation, *trait affect*, self-efficacy). Each moderator will be assessed individually within a logistic regression for the 24-month assessment and within a GEE model by adding the moderator and the interaction term for the moderator and condition. The GEE models will also include interaction terms for the moderator with time and with the time x condition interaction.

Significant interaction terms in a GEE model will be further explored using time-specific analyses. Significant interaction terms for the logistic regression at 24 months will be explored by assessing condition differences for each level of categorical moderators.

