**Specific Aim 1: To test the efficacy of a Spanish-language extended self-help intervention compared to usual care.**

Participants in the first arm will receive the Spanish-language version of the *Stop Smoking for Good* (SS-SP) intervention distributed over 18 months. Those in the second arm, Usual Care (UC), will receive a single, credible, NCI-produced Spanish-language self-help booklet. Outcomes will be assessed through 24 months.

Hypothesis 1: The SS-SP booklets, compared with UC, will produce higher rates of tobacco abstinence than

will be maintained through the 24-month assessment.

**Secondary Aim: To evaluate moderator variables that may aid in refining and targeting of the intervention to maximize impact.**

Demographic moderator variables include gender, age, income, *country of origin*, and generational status. Psychological moderators include nicotine dependence, acculturation, cessation motivation, *trait affect*, and cessation self-efficacy. Moderator analyses will be exploratory, without strong a priori hypotheses.

**Public Health Significance:** This would be the first study to test a Spanish-language adaptation of a validated and easily implemented self-help smoking cessation intervention in a nation-wide RCT, with the potential to reduce ethnic health disparities associated with tobacco smoking.

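### Aim 1 has two primary analyses, each sized at a full two-sided .05, with no rule linking them and no named GEE contrast

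*Combined protocol and SAP*

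**What the plan says.** D3.7.2 describes the primary statistical analyses in the plural. They assess efficacy "in producing smoking cessation compared to Usual Care (UC) in two ways", listed as "1) across all 4 follow-ups using generalized estimating equations (GEE), and (2) at the 24-month follow-up using logistic regression". Power above .80 is targeted once, "with alpha=.05 and a 2-sided test", and two sample sizes follow: 322 per group for the GEE and 365 per group for the logistic regression. The larger was rounded up to 370. Enrolment has since been raised to 1400, or 700 per arm.

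D3.7.4 gives the GEE terms as condition, "time (months from baseline), and the interaction of condition and time". It says the model allows for "assessment of changes in abstinent rates over time and group differences in changes", and then: "Logistic regression will be used to assess condition differences at the 24-month (final) follow-up". It does not say which coefficient or contrast decides Aim 1.

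Hypothesis 1 predicts higher abstinence with SS-SP and ends "will be maintained through the 24-month assessment". The sentence is broken in the text available. The section on primary and secondary outcome measures does not rank the two analyses, and no interim efficacy analysis is planned.

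**The concern.** Two things are left open. The first is the success rule. With two primary tests of one aim, the false-positive rate of the efficacy claim depends on whether one significant result is enough or both are needed. The plan also does not say what is concluded if the two disagree.

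The second is the GEE contrast. D3.7.2 describes an effect over all four follow-ups. The D3.7.4 model contains an interaction, so no single printed coefficient is that effect. If time enters as a continuous term counted from baseline, the condition coefficient is the difference extrapolated to month 0. If time is categorical, it is the difference at whichever visit is the reference. An analyst who reads off the condition line would be testing something other than what was planned, and the choice could be made after the results are seen.

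**Working it through.** **Inputs (D3.7.2).** UC abstinence .123, .152, .191, .198 and SS-SP .152, .230, .269, .288 at months 6, 12, 18 and 24; AR(1) correlation 0.7; alpha .05 two-sided; power .80. 700 per arm is from the randomisation paragraph in D3.2. Covariates and imputation are ignored. GEESIZE was not run.

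**1. Which alpha does 365 use?** Pooled two-proportion formula, with mean rate .243 and difference .090:

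n = [1.960·√(2·.243·.757) + 0.842·√(.198·.802 + .288·.712)]² / .090² = (1.189 + 0.508)² / .0081 ≈ 356 per group.

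The log-odds form gives (1.960 + 0.842)²·(1/.1588 + 1/.2051) / .4937² ≈ 360. With alpha .025 (2.241 in place of 1.960) the pooled formula gives 431. The stated 365 fits an undivided .05 and not a split.

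**2. Which GEE contrast does 322 fit?** For a contrast with log-odds effect δ and variance v (per one participant per arm), n = 7.85·v/δ² and power at N per arm = Φ(δ/√(v/N) − 1.960). For example, the four log odds ratios are .245, .511, .444 and .494, mean .423. With v = 8.93, n = 7.85·8.93/.423² ≈ 391. Ranges below come from two ways of computing the GEE limit: weighted least squares on the planning logits, and solving the GEE with a robust variance.

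| GEE contrast | N/group for 80% power | Power at 700/arm |
|---|---|---|
| 24-month difference, linear time | 323-333 | 98% |
| Common condition effect, no interaction | 336-362 | 97-98% |
| Average of the four visits | 391 | 96% |
| Condition coefficient (month 0), linear time | 3,040-3,870 | 22-27% |
| Condition x time, linear time | 3,080-3,850 | 22-27% |

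The stated 322 belongs with the first rows and cannot be the interaction. The closest is the linear-time 24-month contrast. That does not prove which contrast was used.

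**3. Family-wise error if either test suffices.** 1 − P(|Z1| < 1.960, |Z2| < 1.960), where Z2 is the 24-month log-odds test and r is the correlation between the two under AR(1) 0.7:

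| GEE contrast | r | Either significant | Both significant (no effect at all) |
|---|---|---|---|
| 24-month, linear time | .989-.995 | 5.5-5.7% | 4.3-4.5% |
| Common effect | .87-.88 | 7.2-7.3% | 2.7-2.8% |
| Visit average | .75-.77 | 8.0-8.1% | 1.9-2.0% |

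For the visit average, a true AR coefficient of 0.5 gives 8.7% and 0.9 gives 7.0%. The both-significant column holds only when neither effect exists. If one is real, the error of a both-required rule can approach 5% but not exceed it.

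**4. Disagreement.** With the visit average at the planning rates, 700 per arm and complete data, both tests succeed in about 95% of trials and exactly one in about 4%.

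**The case against.** A reader might infer that D3.7.4 makes condition x time a rival primary test with roughly one-in-four power. The documents do not support that. D3.7.2 defines the primary GEE as an efficacy test over the follow-ups and sizes it at 322, about a tenth of what the interaction would need. D3.7.4 says only what the model will allow to be assessed. The part that stands is narrower: the written model does not itself deliver the intended effect, so the contrast has to be named.

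A reader might also infer that the trial runs at 8% error or more. That holds only if either test is enough and the GEE contrast is the visit average. The contrast closest to the plan's own sample size is almost the same test as the 24-month logistic regression, so the inflation there is about half a percentage point. Hypothesis 1 can be read as requiring both an effect and its maintenance, which would mean no inflation. But the sentence is incomplete in the text available, and nothing in the analysis sections turns it into a testing rule.

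Finally, both analyses use the same endpoint and arms, there is no interim look, and power is ample. All true. Power still does not fix the error rate or say what to conclude when the tests disagree.

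**Conclusion.** The gap is real and moderate in size: two primary tests at a full .05 each, no success rule and an unnamed GEE contrast. Under an either-test rule the family-wise error is about 5.5% to 8.1% at AR(1) 0.7, depending on the overall-effect contrast. Under a both-required rule it is at most 5%. Among the overall or 24-month contrasts the choice hardly affects power at 700 per arm (96-98%). Reading the raw condition coefficient instead would cut it to about 23% (22-27% by method) if time is linear, which the plan does not state.

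These figures assume that the planning rates and working correlation are true and that data are complete. D3.7.2 reports higher-than-expected attrition but gives no measure of information loss. As one assumed scenario, a 30% loss (700 × 0.7 = 490 per arm) gives the visit average 88% power, both tests 84%, and disagreement in about 10.5% of trials. The sample size itself is not in question.

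**What to change.** Before analysis, amend D3.7.2 and D3.7.4 in two respects.

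1. Name the GEE efficacy contrast: an overall condition effect over months 6 to 24, written as an explicit contrast, not the raw condition coefficient and not the interaction. State how time is coded. Report condition x time as supportive.
2. State one rule that holds 5%. One example is a fixed sequence at two-sided .05: the overall GEE contrast first and, only if it is significant, the 24-month logistic comparison as the maintenance claim. This follows the order suggested by Hypothesis 1. Testing 24 months first, a single primary test, requiring both, or .025/.025 would also hold 5%.

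The cost is a few sentences and one contrast statement in the program, with no extra participants. There are two downsides. The second test carries no confirmatory claim if the first fails. And the stated 322 must be restated for the contrast chosen: the visit average needs about 391 per group for 80% power, so it has 78% at 370 per group and about 96% at 700 per arm with complete data. A .025/.025 split would leave about 93% (visit average) and 95% (24 months) at 700 per arm.

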Inclusion criteria will be confirmed with data provided in the baseline assessment. Participants who do not meet criteria based on baseline assessment will be withdrawn. Given that participants provided responses during the initial telephone contact that met the inclusion criteria, we created rules for 4 of the 5 inclusion criteria that required strong evidence from the baseline survey for exclusion. The rules acknowledge that participants may mark unintended responses.

Exclusion criterion #1: Insufficient smoking (<5 cigs per week) or have recently quit.

Rule #1: Page 4, Item 1 response is 'I have not smoked any in the past week'

Rule #2: Page 4, Drop if 2 of the following 3 items have the marked response.

- a) item 2 = 'No use in past month'
- b) item 3 = 'No use in past month'
- c) item 4 = 'Do not smoke'

Rule #3: Page 4, responses to items 2 & 3 show less than 5 cigs per week.

Exclusion criterion #2: Less than 18 years old.

Rules #1: Page 1, Date of birth is less than 18 from date of survey completion.

Exclusion criterion #3: Currently enrolled in an 'in-person' cessation program.

Rule #1: From Quit Aids section on page 10, marked 'Currently Use' for In-person counseling or support program.

Participants will be randomized into the two arms (700 each) using balanced-permuted block, stratified by: sex, smoking rate (daily vs. non-daily smoking), and income (household income < \$10,000). We are stratifying on income based on previously observed treatment effects for our self-help interventions that were moderated by income. Specifically, low-income participants derived greater benefit from the intervention ([name] et al., 2012). Our smoking inclusion and stratification criterion are based on research demonstrating higher rates of non-daily and light smoking (e.g., less than 10 cigarettes per day) among Hispanic/Latinos (e.g., Kaplan et al., 2014, Okuyemi et al., 2002) and that different reasons for smoking exist among Hispanic/Latinos based on smoking level (Pulvers et al., 2014). To minimize treatment contamination, participation will be limited to one participant per household address.

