### **Data Acquisition and Data Entry**

Participants will be randomized into the two arms (700 each) using balanced-permuted block, stratified by: sex, smoking rate (daily vs. non-daily smoking), and income (household income < \$10,000) and data will be collected via (1) paper and pencil measures or (2) secure internet websites managed by Moffitt's Survey Core. Data from paper and pencil measures will be input through screens created by the Data Systems Team within Moffitt's Research Computing Support Group (Research IT) and will be subject to computerized range and consistency checks. The data will then populate an Access database, which will also be created and maintained by Research IT. This process will be supervised jointly by the PI and Study Data Manager/Statistician. The database will be converted on a monthly basis to a SAS database (SAS Institute, Cary, NC). This database and SAS will be used by the statistician who will provide the PI with reports and summaries on a regular basis and perform the final analyses.

To ensure participant confidentiality, baseline and follow-up assessment data will not include any unique identifiers.

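### Covariates for both primary models are picked by baseline group differences, so the stratification factors are left out and the covariate list is not fixed in advance (modest harm)

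*Combined protocol and SAP*

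**What the plan says.** The rule appears twice. The overview in D3.7.3 compares the arms on baseline measures and says that "any variable that exhibits a significant group difference will be incorporated into the primary analyses". D3.7.4 then says of both primary models that "potential confounding variables (e.g., group differences on demographic variable) that appear despite randomization will be included". The only terms fixed in advance are condition, time and their interaction in the GEE model, and condition in the 24-month logistic regression.

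D3.2 describes permuted-block randomisation "stratified by: sex, smoking rate (daily vs. non-daily smoking), and income" (household income below $10,000), and the Data Acquisition and Data Entry section repeats this. No section carries these factors into a primary model.

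Baseline predictors of smoking appear in two other roles. In D3.7.3 they serve the imputation model, as "auxiliary variables (e.g., baseline measures that predict smoking status at follow-up) to be determined by preliminary analyses". Under the Secondary Aim in D3.7.4 they serve as moderators: "Each moderator will be assessed individually within a logistic regression for the 24-month assessment". The Specific Aims describe that work thus: "Moderator analyses will be exploratory, without strong a priori hypotheses".

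**The concern.** A covariate helps a randomised comparison when it predicts the outcome. Whether it happens to differ between arms is a separate matter, because under randomisation any such difference is chance. The rule therefore selects on the wrong property. It also works against the design: stratified blocking forces balance on sex, smoking rate and income, so the factors thought important enough to stratify on are the ones the screen cannot find.

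Three things are at stake.

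- **Precision.** The rule should perform about like no adjustment at all.
- **Calibration.** If the strata predict abstinence, standard errors that ignore the stratified allocation are too large and the test is conservative.
- **Reproducibility.** D3.7.3 gives no significance level for the screen and no list of variables. D3.7.4 names no test. Two analysts could fit different primary models, and the set is settled only after baseline data by arm have been seen.

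**Working it through.** **The plan's own figure.** D3.7.2 gives 24-month rates of 19.8% and 28.8%, two-sided alpha .05, power above .80, and 365 per group. The pooled two-proportion formula is

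n = [1.96·√(2·.243·.757) + 0.842·√(.198·.802 + .288·.712)]² / .09² = 356 per group.

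Variants give 353 (unpooled), 360 (log-odds) and 378 (continuity-corrected), so 365 is reproduced within 3%. Power is .810 at 365 and .976 at 700 per group.

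**Can the screen select a stratification factor?** Three binary factors make 8 strata, so each level of a factor covers 4. The block size b is not stated. An unfinished block leaves at most b/2 excess in a stratum, so at most 2b per level. In the worst case the two levels are out of balance in opposite directions. For a factor with prevalence π at 700 per arm,

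max |z| = (2b/700) / √[2π(1−π)/700].

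For b = 4 and π = .5 this is .01143/.02673 = 0.43; for π = .1 it is .01143/.01604 = 0.71. For b = 10 the range is 1.07 to 1.78. A difference at p < .05 is impossible for blocks up to 10 (π from 10% to 50%) and becomes arithmetically possible only from about b = 12 at π = 10%. In simulated allocations none of 1,500 trials selected a factor at b = 2, 4, 8 or 16.

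**Does something else enter by luck?** With 22 independent baseline measures screened at 5% (both assumed), the chance is 1 − 0.95^22 = .676.

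**Effect on the 24-month logistic test.** The documents give no prognostic strengths, so four settings were assumed. Prevalences were .5 (sex), .7 (daily smoking) and .35 (low income), with blocks of 4 and 22 baseline measures, 2 of them prognostic. Log odds ratios for sex, daily smoking and income, then per SD of each of the 2 covariates, were:

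- weak: .1, .4, .3; .2
- moderate: .2, .6, .4; .3
- strong: .3, 1.0, .6; .5
- very strong: .6, 1.5, 1.0; .5

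Each setting had 10,000 trials at the planned rates, or at 24.3% in both arms for type I error. Results at 700 per arm:

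| | Unadjusted | Rule | Strata | Strata + 2 |
|---|---|---|---|---|
| Power, weak | .975 | .974 | .975 | .977 |
| Power, moderate | .980 | .981 | .980 | .985 |
| Power, strong | .977 | .978 | .979 | .988 |
| Power, very strong | .980 | .980 | .985 | .990 |
| Type I, weak | .048 | .048 | .050 | .051 |
| Type I, moderate | .052 | .051 | .055 | .054 |
| Type I, strong | .044 | .043 | .049 | .049 |
| Type I, very strong | .037 | .035 | .049 | .050 |

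Over all 12 logistic settings (120,000 trials, including 370 per arm) the rule never selected a stratification factor. At 700 per arm under the null, the ratio of mean model standard error to empirical SD under the rule was 1.01/1.00/1.03/1.07 (weak to very strong), against 1.00/0.98/1.00/1.00 with strata + 2. The variance of the risk difference, relative to no adjustment, changed by +0.1/−0.4/−1.3/−1.1% under the rule and by −1.6/−2.7/−8.4/−7.7% with strata + 2.

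**Effect on the GEE test.** This used the planned rates at all four visits, latent AR(1) correlation 0.7, robust standard errors with independence working correlation, and a common condition effect. For moderate/strong/very strong, power was .996/.996/.996 under the rule and .998/.998/.999 with strata + 2. Type I error was .048/.038/.031 and .055/.050/.055.

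**Check under other assumptions.** With prevalences of 50/25/30% and odds ratios per factor from 1.2 up to 2/3/2, type I error under the rule was .043 to .049. Adjusting for the strata alone added 0.1 to 0.4 points of power at 700 per arm.

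**The case against.** The strongest reply is that the rule does little damage. Restoring the strata alone at 700 per arm changes logistic power by +0.1/−0.1/+0.1/+0.5 points. Three of these are below the Monte Carlo error of one estimate (about 0.15 point), and the fourth needs an odds ratio of about 4.5 for daily smoking (e^1.5). The larger gains come mainly from two hypothetical prognostic covariates. Significance differs between the rule and the fixed list in only 0.5 to 1.1% of trials under the planned effect. All of this stands, and it sets the size of the point.

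A screen on baseline data, stated in advance, also leaves no room for outcome-driven choice. That is fair for D3.7.3. The latitude lies in the D3.7.4 wording and in the missing level and list.

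An analyst could add sex or income under D3.7.4 by judgement. But that text also depends on differences that arise despite randomisation, which blocking prevents for these factors. Related measures, such as finer income categories, could still enter by chance.

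The simulations are not the full planned analysis. They have complete outcomes and no imputation, although D3.7.2 reports higher attrition than expected without giving a rate. The GEE runs omit the planned interaction, treat time as categorical and do not use the AR(1) working structure. Type I error of .055 for the adjusted GEE in the very strong setting is about 2.4 Monte Carlo standard errors above .05. These limits stand: the figures indicate size and are not forecasts.

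**Conclusion.** The concern holds and is minor. Both primary models choose covariates by a property unrelated to prognosis, omit the stratification factors, and leave the covariate set open until baseline data by arm are examined. The result is valid but about as efficient as no adjustment: within 0.1 point of unadjusted logistic power at 700 per arm. The rule captures at most about 15% of the variance reduction that the fixed list gives. Type I error is not inflated, and it becomes conservative only when the strata are strongly prognostic.

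For context only, at the earlier requirement ("The final sample size for analyses was rounded up to 370 per group") the fixed list raises power from .806 to .818 in the weak setting and from .829 to .885 in the very strong one. The planned analysis uses all 1,400 participants, so this does not add to the severity. Block size, prevalences, prognostic strengths and the number of screened measures are assumptions. The stated 365 per group need not change.

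**What to change.** Delete both baseline-difference rules. In the GEE model and the 24-month logistic regression, include sex, daily versus non-daily smoking and household income below $10,000, plus a short named list of baseline covariates already collected. The Fagerström score and the Contemplation Ladder in D3.4.1 are possible examples. Put the same variables and condition in the imputation model, and keep the unadjusted model as a sensitivity analysis.

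The choice must be dated and documented as made without sight of outcomes by arm. D3.4.1 shows that some 12-month disconfirmation results are already known, and baseline data by arm may also have been seen, so blinding to outcomes by arm is the safeguard still available.

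The cost is a few sentences and no new data. The downside is that the adjusted odds ratio is conditional. At 700 per arm and the planned effect, its mean log was 0.51 to 0.61 with strata + 2, against 0.49 to 0.50 unadjusted, with a standard error 2 to 12% larger. It should be labelled as such; a standardised marginal effect alongside it is optional.

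### The GEE across all four follow-ups is the first primary efficacy analysis, but the plan ties no contrast, time coding or link to it

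*Combined protocol and SAP*

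**What the plan says.** Section D3.7.2 says the primary analyses will assess efficacy in two ways: "1) across all 4 follow-ups using generalized estimating equations (GEE), and (2) at the 24-month follow-up using logistic regression". Hypothesis 1, under Specific Aim 1, is that the booklets, "compared with UC, will produce higher rates of tobacco abstinence". It also speaks of maintenance through the 24-month assessment, although that sentence is broken in the available text.

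Section D3.7.4, under Specific Aim 1, gives the GEE as a population-averaged model "with the main covariates of intervention condition (UC vs. SS-SP), time (months from baseline), and the interaction of condition and time". It then states the model's use: "The GEE analysis will allow for assessment of changes in abstinent rates over time and group differences in changes". The next sentence gives the second primary analysis a definite target: "Logistic regression will be used to assess condition differences at the 24-month (final) follow-up".

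On size, D3.7.2 says that with an "AR(1) working correlation structure and coefficient of 0.7, sample size was estimated at 322/group for the GEE analyses". It does not say which contrast that figure is for. Neither section states the link function, or whether time enters as linear months or as categorical visits.

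**The concern.** Efficacy across all follow-ups is a question about the level of abstinence in one arm against the other. Once condition x time is in the model, the condition coefficient is no longer an overall effect:

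- With linear months from baseline, it is the arm difference extrapolated to month 0, which is not a follow-up, and the interaction is a difference in slope.
- With categorical visits and month 6 as reference, it is the month-6 difference alone.

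A sound efficacy test can be built from the same model, but none is named. The logistic regression is tied to a condition difference; the GEE is tied only to change. The deciding test for one of two primary analyses could therefore be chosen after the data are seen, or the printed coefficients could be read as they stand. The plan assumes a mostly sustained level difference, so those two routes differ greatly in power.

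**Working it through.** **Inputs (D3.7.2 and the design sections).** Abstinence at 6, 12, 18 and 24 months: UC 12.3, 15.2, 19.1, 19.8%; SS-SP 15.2, 23.0, 26.9, 28.8%. AR(1) correlation 0.7, 2-sided alpha 0.05, 700 per arm. Assumed: logit link, complete data, true correlation equal to the working one.

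**The plan's own figures.** The 24-month comparison (19.8% v 28.8%, 80% power) gives 356 per group with the two-proportion formula and 360 with a logit Wald test, against the stated 365. That is close. Its power at 700 per arm is 97.4% (logit Wald).

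The GEE figure of 322 cannot be reproduced uniquely, because its contrast is not given. Closed-form weighted least squares on the planned logits gives 321.5 per group for a model with condition only, and 322.7 for the month-24 contrast of the D3.7.4 model with linear months. Fully iterated GEE gives 391.1 and 332.5. The month-0 and slope terms each need more than 3,000 per group by either method.

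**Assumed effect.** Log-odds ratio at each visit = logit(SS-SP) - logit(UC): 0.245, 0.511, 0.444, 0.494. Mean = 1.694/4 = 0.423.

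**Power.** z = estimate/SE at 700 per arm; power = Φ(z - 1.96) + Φ(-z - 1.96). Iterated GEE with linear months and sandwich variance:

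- Month-0 condition term: 0.2263/0.1879 = 1.204, power 22.6%.
- Slope difference: 0.0117 per month, z = 1.335, power 26.7%.
- Average over the four visits (mean month = (6 + 12 + 18 + 24)/4 = 15): 0.2263 + 15 x 0.01172 = 0.402; SE 0.1121, z = 3.585, power 94.8%.
- Average with categorical visits: 0.423/0.1129 = 3.75, power 96.3%.

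| Test | Power, 700 per arm | n per group for 80% |
|---|---|---|
| Month-0 condition term | 22.6% (closed form 26.9%) | 3,789 (3,042) |
| Slope difference | 26.7% (22.3%) | 3,083 (3,851) |
| Month-6 coefficient, categorical visits | 35.0% | 2,221 |
| Average, linear months | 94.8% (96.2%) | 427 (395) |
| Average, categorical visits | 96.3% | 391 |
| Joint condition and interaction, 2 df | 96.6% (97.3%) | 398 (380) |
| Joint test of four visit effects, 4 df | 97.4% | 389 |
| Common effect, no interaction, linear months | 97.4% | 362 (336) |
| Common effect, no interaction, categorical visits | 97.9% | 346 (352) |

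**Simulation.** In 4,000 trials with 700 per arm, estimated AR(1) and sandwich Wald tests, rejection was 22.4% for month 0, 27.5% for slope, 95.3% (linear) and 96.3% (categorical) for the average, and 97.3% for the joint 2-df test. With equal arms the averaged contrast rejected 5.1% (linear) and 5.0% (categorical).

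**Other correlations (power at 700 per arm, iterated).**

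| Correlation | Month 0 | Slope | Average, linear | Average, categorical |
|---|---|---|---|---|
| AR(1) 0.5 | 23.9% | 20.7% | 98.8% | 99.0% |
| Exchangeable 0.7 | 41.6% | 42.3% | 94.9% | 93.8% |
| Exchangeable 0.5 | 39.4% | 28.4% | 97.8% | 97.4% |

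**Other link.** On an identity link (closed form, AR(1) 0.7), the slope difference has 79% power, the month-0 term 6% and the linear-month average 95.4%. The low slope figure is therefore specific to the logit link.

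**The case against.** The strongest reply is that the GEE does have an efficacy purpose. D3.7.2 gives it one, the Aim 1 heading is about testing efficacy, and the D3.7.4 sentence on change says what the model allows, not all that it is for. This stands. The gap is that the purpose is never turned into a test.

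A reader might infer that the model answers a different question from Hypothesis 1. That goes too far: the condition x time term bears on the part about maintenance through 24 months, and the condition term is in the model.

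A reader might also infer that the first primary analysis has only about a quarter of the power it needs. The documents do not say that efficacy will be judged on a single coefficient. The 22-27% figures describe one direct reading, under an assumed link and linear, uncentred months.

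Finally, 322 might be called wrong, or taken as evidence of a condition-only model that conflicts with D3.7.4. It fits the month-24 contrast of the planned model (322.7) as well as a condition-only effect (321.5), so it supports neither claim.

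The choice among suitable tests is partly preference: averaged, joint and common-effect tests all address the aim.

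**Conclusion.** The concern holds as a gap in specification that should be closed before analysis. The first primary analysis is meant to test efficacy over four follow-ups, but the section defining it names no contrast, time coding or link and mentions only change. Under the plan's rates with AR(1) 0.7, complete data, a logit link and linear months, the two condition-related terms read directly have about 22-27% power at 700 per arm, and suitable efficacy contrasts about 95-98%. Under the other correlations tried, the direct terms reach at most about 42% and the averaged contrast stays at 94-99%. The exact figures for the direct terms depend on the unstated link and coding; that an averaged contrast is well powered does not. Information lost to missing data would lower all of these figures.

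This is not a finding that the trial is too small or that the 24-month analysis is affected.

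**What to change.** Keep the planned model. In D3.7.4, before analysis:

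- State the link and how time is coded.
- Name one 2-sided 0.05 GEE efficacy test. A suitable choice is the condition effect averaged equally over months 6, 12, 18 and 24: condition + 15 x interaction with linear months, or the mean of the four visit-specific condition effects with categorical visits. A joint test of condition and interaction would also serve.
- Report condition x time as a secondary description of whether the difference is maintained.

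In D3.7.2, state the contrast behind 322 per group. If the averaged contrast is chosen, restate the GEE requirement as about 391 (categorical visits) to 427 (linear months) per group. Part of the linear-month figure is calculation method, since the closed form gives 395.

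**Cost.** Wording only; no extra participants, data or models. The stated GEE size becomes less favourable and passes the 370 per group to which D3.7.2 rounded, but D3.7.4 analyses all 1,400 participants, 700 per arm. The averaged contrast gives month 6, where the assumed effect is smallest, full weight, so its power is 94.8-96.3% against 97.4-97.9% for a common effect. With linear months it also leans on linearity (0.402 against 0.423 for the mean of the four visit log-odds ratios).
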